4.2 Selection of Study Population

The study population included subjects who completed the SM04690-OA-11 study. Complete inclusion/exclusion criteria are available in the study protocol.

4.3 Method of Treatment Assignment and Randomization

Subjects were randomized in the SM04690-OA-11 study. Each subject maintained the same treatment assignment of LOR or placebo as in the parent study at Visit 1E (Day 1). At Visit 3E

(Week 48) and for any subsequent injections until the Termination Visit, all subjects received LOR injection(s).

4.4 Treatment Blinding

Subjects consented in this study were previously treated with an IA injection of either LOR or placebo in their target knee in the SM04690-OA-11 parent study that was double-blinded. The blind for the subject's previous treatment with either LOR or placebo will be maintained in this study for Investigators, site personnel, and subjects only. Sponsor was unblinded to treatment assignment once the database from the parent study was locked. At Visit 1E (Day 1), preparation of LOR or placebo for injection and the administration of the injections were to be performed by an Unblinded Investigator who had minimal contact with the subject for other aspects of the study. At Visit 3E (Week 48) and for any subsequent injections, the LOR injections did not need to be performed by a designated Unblinded Investigator due to the open-label nature of the remaining portion of the study.

4.5 Minimization of Missing Data

4.5.1 Collection of Clinical Outcomes

Clinical outcomes data were collected on paper at each applicable study visit. Upon completion of each assessment and questionnaire, the subjects were to sign or initial, then date the source documents to indicate that they were reported accurately.

4.5.2 Rescue Medication

Subjects were allowed to use NSAIDs and/or acetaminophen for pain relief as needed (see Protocol Section 7.8). If a subject's clinical condition significantly deteriorated (defined as experiencing significant pain that cannot be satisfactorily controlled using NSAIDs and/or acetaminophen), the Investigator would consult with the Medical Monitor(s). Sites were instructed to capture the amount and frequency of rescue medication use. This policy, in addition to quantifying NSAIDs and/or acetaminophen medication use, was designed to minimize the loss of key endpoint data and provide assessment of the medication's impact on key endpoint data.

4.5.3 Prohibited Medications, Treatments, and Procedures

During the conduct of the study, certain medications, treatments, and procedures were prohibited (see Protocol Section 7.6). The overall intent of these prohibitions was to minimize any possible bias in the assessment of the clinical trial endpoints. However, the protocol did allow for the use of these prohibited therapies if, and only if, they were required to ensure subject safety. Investigators were instructed to notify the sponsor's Medical Monitor, who would note the prohibited therapy as a protocol deviation. These deviations were categorized as major or minor depending on the nature and timing of the interventions. Subjects were not automatically discontinued based upon prohibited therapy use, allowing for continued data collection and assessment of the impact of prohibited therapy on key endpoint data.

4.5.4 Intermittent Missing Data

Ongoing programmatic surveillance of eCRFs and visit compliance using intranet dashboards during trial conduct led to the identification of subjects that were not compliant with the protocol. Sites were notified of possible non-compliant subjects and were instructed to address

any possible technical or conduct issues with these subjects prior to key endpoint data collection times. The ongoing monitoring of eCRFs was a specific strategy designed to minimize the loss of key endpoint data.

5. SAMPLE SIZE DETERMINATION

The sample size of up to approximately 500 subjects was estimated based on practical considerations, such as the number of subjects anticipated to complete study SM04690-OA-11, but there was no set cap on enrollment.

6. ANALYSIS POPULATIONS

6.1 Full Analysis Set

The Full Analysis Set (FAS) includes all subjects who received a study injection in the current study, analyzed as randomized in the parent study.

6.2 Per-Protocol Analysis Set

The Per-Protocol Analysis Set (PPAS) includes FAS subjects who received the correct treatment, completed Visit 6E (Week 100) and did not have any major protocol deviations in the current or parent study that might impact the evaluation of efficacy outcomes (see [Section 8.2](#)). Subjects will be analyzed as randomized for the PPAS.

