3.2 Study Endpoints

3.2.1 Primary Efficacy Endpoint

Change from parent-study baseline medial joint space width (mJSW) in the target knee as evaluated by radiograph at Visit 3E (Week 48)

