6.4 Modified Full Analysis Set

The Modified Full Analysis Set (mFAS) includes all FAS subjects who completed Visit 3E (Week 48).

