6.5 Completers Analysis Set

The Completers Analysis Set (CAS) includes all FAS subjects who have an mJSW result at Visit 6E (Week 100) (including a parent-study baseline value).

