8.2 Protocol Deviations

A protocol deviation is defined as any noncompliance with the clinical trial protocol requirements. The noncompliance may be either on the part of the subject, the Investigator, or the study site staff.

Deviations are summarized into one of the following categories:

- Informed Consent Form
- Enrollment
- Procedures
- Labs/Specimens
- Study Visits
- Investigational Product
- Subject Non-Compliance
- Serious Adverse Events

Deviations are categorized as major or minor by a cross-functional team according to pre-defined criteria established in the Protocol Deviation Classification Guideline.

- A major deviation is defined as a divergence from the protocol that materially (a) reduces the quality or completeness of efficacy data, (b) makes the informed consent inaccurate, or (c) impacts a subject's safety, rights or welfare.
- A minor deviation is defined as a divergence from the protocol that deviates from the procedures and guidelines outlined in the protocol, but is not classified as a major deviation (i.e. the deviation does not materially (a) reduce the quality or completeness of the data, (b) make the informed consent inaccurate, or (c) impact a subject's safety, rights or welfare).

Protocol deviations may result in subject exclusion from the PPAS. All protocol deviations were reviewed by study team members to determine if the deviation could reasonably affect/confound interpretation of key efficacy endpoints and should result in the subject being excluded from the PPAS. 27 subjects (29 protocol deviations) with the following types of deviations were excluded from PPAS:

- Major parent study protocol deviation impacting efficacy outcome(s):

- Major EN01 deviations (subject randomized or enrolled without meeting eligibility criteria): n = 3
- Major NC03 deviations (prohibited procedure done): n = 2
- Major OA-07 study protocol deviation impacting efficacy outcome(s):
 - Major NC03 deviations (prohibited procedure done): n = 1
 - Major NC04 deviations (prohibited concomitant medication taken) that would affect efficacy analysis at Visit 3E (Week 48) or Visit 6E (Week 100): n = 5
 - Major P01 deviations (procedure performed incorrectly): n = 5
 - Major P02 deviations (Procedure not attempted or not performed): n = 13

A final list of protocol deviations resulting in subject or data exclusion from the PPAS can be found in Appendix 1 – Protocol Deviations Leading to Exclusion from Per-Protocol Analysis.

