9.4 Primary Efficacy Analysis

9.4.1 Main Analysis

Parent-study baseline-adjusted ANCOVA will be used to assess the change in mJSW at Visit 3E (Week 48) in the FAS.

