9.4.2 Sensitivity Analysis

Missing data will be imputed using the MI method as described in Section 7.1.4. The main primary analysis will also be repeated for subjects in the mFAS, CAS, and PPAS.

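### The per-protocol and completers sets used to check the Week 24 and Week 48 results require attendance or data at Week 100, so they select subjects on open-label events after the endpoint

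*SAP*

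**What the plan says.** The primary endpoint is "Change from parent-study baseline medial joint space width (mJSW) in the target knee as evaluated by radiograph at Visit 3E (Week 48"). The secondary endpoints are at Visits 2E and 3E (SAP 3.2.2). From Visit 3E onward every subject receives open-label LOR (SAP 4 and 4.3).

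The analysis sets are tied to different visits:

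- The PPAS (SAP 6.2) "includes FAS subjects who received the correct treatment, completed Visit 6E (Week 100) and did not have any major protocol deviations".
- The CAS (SAP 6.5) "includes all FAS subjects who have an mJSW result at Visit 6E (Week 100) (including a parent-study baseline value").
- The mFAS (SAP 6.4) "includes all FAS subjects who completed Visit 3E (Week 48").

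The main primary analysis does not use these sets: "Parent-study baseline-adjusted ANCOVA will be used to assess the change in mJSW at Visit 3E (Week 48) in the FAS" (SAP 9.4.1). The sensitivity section then says: "The main primary analysis will also be repeated for subjects in the mFAS, CAS, and PPAS" (SAP 9.4.2). Section 9.5.2 does the same for the secondary endpoints, and Section 9.6 for the other efficacy analyses.

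SAP 8.2 excludes 27 subjects (29 deviations) from the PPAS. Its prohibited-medication line counts deviations "that would affect efficacy analysis at Visit 3E (Week 48) or Visit 6E (Week 100): n = 5".

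**The concern.** A sensitivity set for a Week 48 contrast should be fixed by what happened up to Week 48. Here, membership of the PPAS and CAS is settled about a year later, after the placebo arm has crossed over. Someone with a good Week 48 radiograph and no deviations drops out of both repeats for leaving afterwards. The CAS requires a Week 100 radiograph even when the endpoint is Week 24 pain. The mFAS has a milder form of the same fault: it makes Week 24 analyses depend on attending Week 48.

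Later exit need not be unrelated to the Week 48 result. Protocol 5.6.1 lists lack of efficacy, adverse events and target-knee replacement among the reasons for discontinuation. The arms also enter the open-label year differently: former placebo subjects get their first LOR dose, LOR subjects a further one. If exit depends on outcome differently by arm, the PPAS and CAS contrasts can move through selection alone. A reader could then mistake agreement or disagreement with the FAS for evidence about robustness.

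The SAP does not make this visible. Appendix 2 lists the PPAS as Sensitivity 3 for the Week 48 primary estimand and describes only the prohibited-medication exclusion. The CAS has no row there. SAP Section 13 records the new mFAS and CAS, but not the PPAS change from completing the study (Protocol 10.3) to completing Visit 6E.

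**Working it through.** **1. Timing.** Week 100 − Week 48 = 52 weeks after the primary endpoint. With the ±4-week windows the gap runs from (100 − 4) − (48 + 4) = 44 to (100 + 4) − (48 − 4) = 60 weeks. For the Week 24 secondaries it is 100 − 24 = 76 weeks.

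**2. One subject, four sets.** Take a correctly treated subject with baseline and Week 48 radiographs and no deviations, who leaves between Visits 3E and 6E.

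| Set | Included in the Week 48 analysis? |
|---|---|
| FAS | yes |
| mFAS | yes |
| PPAS | no, Visit 6E not completed |
| CAS | no, no Visit 6E mJSW |

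**3. Deviation count (SAP 8.2).** Parent study 3 + 2 = 5; current study 1 + 5 + 5 + 13 = 24; total 29, matching the stated 29. The five parent-study deviations precede Visit 3E, so at most 24 could come after it. How many do is not visible in the text reviewed.

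**4. Precision.** Loss between Visits 3E and 6E is not given, so it is assumed. With a fraction L lost, the standard error in the affected repeats grows by 1/√(1 − L): 1.054 at 10%, 1.118 at 20%, 1.195 at 30%.

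**5. Selection bias, illustrative.** Assumptions: the baseline-adjusted Week 48 outcome Y is standard normal, higher is worse, and the true difference is 0. Exit before Week 100 follows logit P(exit) = a + bY, with b allowed to differ by arm. Bias = E[Y | retained, LOR] − E[Y | retained, placebo]; negative favours LOR. None of the slopes or loss rates comes from the documents.

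| Slope b, LOR / placebo | Loss | Retained means | Bias (SD) |
|---|---|---|---|
| 0.8 / 0.2 | about 26% (a = −1.1) | −0.196 − (−0.050) | −0.146 |
| 0.5 / 0.2 | about 26% (a = −1.1) | −0.124 − (−0.050) | −0.074 |
| 0.8 / 0.2 | 10% each arm | −0.075 − (−0.020) | −0.055 |
| 0.5 / 0.2 | 10% each arm | −0.049 − (−0.020) | −0.029 |
| 0.2 / 0.8 | about 26% (a = −1.1) | −0.050 − (−0.196) | +0.146 |
| 0.5 / 0.5 | equal in both arms | equal | 0 |
| 0.5 / 0.5 | 20% LOR, 30% placebo | −0.096 − (−0.143) | +0.047 |

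With 250 per arm (500 subjects, 1:1 allocation assumed), two-sided 5% and outcome-related exit in one arm only (b = 0.5), the type I error of the repeat is Φ(−1.96 + |bias|/SE) + Φ(−1.96 − |bias|/SE). At 10%, 20% and 30% loss, the bias is 0.049, 0.096 and 0.143 SD in absolute size, the SE is 0.094, 0.100 and 0.107, and the error rate is 8%, 16% and 27%. If exit is unrelated to outcome, or equally related with equal retention, it stays at 5%.

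**The case against.** The strongest reply is that no main result depends on these sets. The primary and secondary main analyses use the FAS. Two other checks avoid the Week 100 condition: multiple imputation in the FAS and, for Week 48, the mFAS. That is correct, and it limits the point to two supplementary repeats. A reader might infer that the primary estimate itself is compromised; the documents do not support that.

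Arm-differential exit is also less likely than it first looks. Sites and subjects stay blinded to earlier treatment (SAP 4.4), everyone gets the same injection at Visit 3E, and active subjects were asked to stay until Visit 6E despite the termination (SAP 4.1). This lowers the probability but does not remove the mechanism. The illustration is also most natural for pain. If exit depended on pain alone, and pain correlated 0.1 to 0.3 with mJSW (an assumption), the mJSW bias would be about 0.003 (0.029 × 0.1) to 0.04 SD (0.146 × 0.3).

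A reader might also infer that subjects were dropped for deviations affecting only Week 100. The wording in SAP 8.2 permits this but does not show it. The itemised appendix is not in the text reviewed, and 8.2 speaks of excluding subjects or data, so some exclusions may apply only to particular data.

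Finally, the protocol's PPAS already required completing the study, so conditioning on later follow-up is inherited. Naming Visit 6E makes the rule clearer after the early termination, but does not suit it to a Week 48 endpoint.

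**Conclusion.** The mismatch is established from the SAP's own definitions: two sets conditioned on Week 100 are used for placebo-controlled endpoints at Weeks 24 and 48. They can discard valid data and cannot serve as clean robustness checks for the blinded period. As written, no per-protocol analysis addresses that period alone.

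The effect on the estimates is hypothetical. Under a true null, bias is 0 when exit depends on outcome equally in both arms with equal retention. It is about 0.03 to 0.15 SD under the assumed arm-differential slopes with 10% to 26% loss. It would be wrong to read this as a bias in favour of LOR: swapping the slopes reverses the sign, and the documents give no retention by arm. Severity is moderate, because only sensitivity analyses are affected.

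**What to change.** - **Week 48 per-protocol set:** FAS subjects correctly treated at Visit 1E, with Visit 3E completed and no efficacy-relevant major deviation (parent study included) up to Visit 3E.
- **Week 24 per-protocol set:** the same rule with a Visit 2E cutoff. Do not use the mFAS as a Week 24 sensitivity set.
- **Week 100:** keep the Visit 6E-based PPAS and the CAS only for Section 9.6.5 and the Visit 6E parts of 9.6.3 and 9.6.4. Remove the CAS from 9.4.2, 9.5.2 and the Week 24 and Week 48 analyses in 9.6.
- **Deviations:** sort the 29 by date against Visits 2E and 3E, from a listing without treatment codes.
- **Record:** align Appendix 2 and enter the redefinition in Section 13.

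The direct cost is SAP wording, extra population flags and one date sort. The change in the number analysed cannot be computed, because no Week 48 or Week 100 completion counts are given. The real drawback is timing: "Sponsor was unblinded to treatment assignment once the database from the parent study was locked" (SAP 4.4), and subjects kept the same assignment at Visit 1E. A listing without codes cannot undo that knowledge, so the change should be settled before results are produced and disclosed as made after unblinding.

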6.3 Safety Analysis Set

The Safety Analysis Set (SAS) includes all subjects who received a study injection in the current study, analyzed as treated in the current study.

6.4 Modified Full Analysis Set

The Modified Full Analysis Set (mFAS) includes all FAS subjects who completed Visit 3E (Week 48).

6.5 Completers Analysis Set

The Completers Analysis Set (CAS) includes all FAS subjects who have an mJSW result at Visit 6E (Week 100) (including a parent-study baseline value).

7. GENERAL ISSUES FOR STATISTICAL ANALYSIS

7.1 General Statistical Methodology

Unless otherwise specified, efficacy analyses will be performed on the FAS, PPAS, and mFAS; general safety, bone imaging, and biomarker analyses will be performed on the SAS. The number of evaluable subjects in any analysis set may vary by endpoint/timepoint based on missing data.

For continuous variables, the outcome measure at each visit, as well as the absolute change (outcome at visit – outcome at baseline), will be summarized within each treatment group using descriptive statistics (number of subjects, mean, SD, median, minimum, and maximum). Categorical variables will be summarized with counts and percentages.

Data collected from unscheduled visits will not be included in summary tables but will be included in subject-level listings as appropriate.

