3.2 STUDY ENDPOINTS

3.2.1 SAFETY ENDPOINTS

- Adverse events (AEs) and serious adverse events (SAEs) (incidence, severity, and relationship to study drug) over the course of the study
- Clinically significant changes from parent-study-baseline clinical laboratory measures and vital signs, as assessed by the Investigator, over the course of the study
- Change in serum bone biomarkers (N-terminal propeptides of procollagen type I [P1NP] and β -C-terminal telopeptide [β -CTX]) from parent-study baseline, and change in a serum cartilage biomarker (cartilage oligomeric matrix protein [COMP]) from parent-study baseline at Visit 3E

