7. STUDY PROCEDURES AND SCHEDULE

7.1 STUDY PROCEDURES/EVALUATIONS

7.1.1 STUDY SPECIFIC PROCEDURES

Collection of Adverse Events Data

Data regarding AEs will be collected in this study. As this is an extension trial, AE collection will continue from the parent study, ongoing AEs at the end of the parent study will continue to be monitored, and new AEs that occur during this study will be recorded. Changes to ongoing

AEs that occur after the parent-study EOS visit will not be recorded in the parent study. AEs will be assessed through the Termination Visit.

Each subject will be observed and queried by the Investigator or designee at each study visit for any continuing AEs or new AEs since the previous visit. The subject may be asked to return to the site for an unscheduled visit if an AE occurs between study visits, and if, in the opinion of the Investigator, the AE requires a study visit for full evaluation. The following information will be recorded within the eCRF for each AE: Description of the event, date of onset and resolution, and severity as assessed by the Investigator according to the Clinical Data Interchange Standards Consortium (CDISC) Severity/Intensity Scale for Adverse Events (AESEV) ([Table 1](#)), causal relationship to study medication, outcome, and any action taken.

In this protocol, signs and symptoms of exacerbation or worsening of target knee OA will be captured in the context of efficacy assessments and recorded on specific pages of the eCRF. Anticipated fluctuations or anticipated deterioration (in the opinion of the Investigator) of the underlying disease (target knee OA) will not be considered as AEs nor captured on the AE eCRF.

Whenever possible, it is preferable to record a diagnosis as the AE term rather than a series of symptoms relating to a diagnosis. Fluctuations of pre-existing conditions that do not represent a clinically significant exacerbation or worsening need not be considered AEs.

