3.2.3 Safety Endpoints

1. Adverse events (AEs) and serious adverse events (SAEs) (incidence, severity, and relationship to study drug) over the course of the study up to the end of the single-blind and placebo-controlled portion of the trial (i.e., prior to Second OA-07 injection [Lorecivivint only])
2. Clinically significant changes from parent-study-baseline clinical laboratory measures and vital signs, as assessed by the Investigator, over the course of the study up to Visit 3E (Week 48)

3. Change in serum bone biomarkers (N-terminal propeptides of procollagen type I [P1NP] and β -C-terminal telopeptide [β -CTX]) from parent-study baseline, and change in a serum cartilage biomarker (cartilage oligomeric matrix protein [COMP]) from parent-study baseline at Visit 3E (Week 48)

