10.2 Clinical Laboratory Evaluations

All chemistry, hematology and urinalysis results from the central laboratory will be summarized into shift tables as normal, non-clinically significant abnormal, and clinically significant abnormal. Assessments of clinical significance for abnormal values were made by the investigator on results that were outside of the normal range. Shift tables will compare the number and percent of assessments from each visit to baseline values for each treatment group.

All chemistry and hematology results from the central laboratory will be summarized for each treatment group. Descriptive statistics of each laboratory test at all timepoints will be provided along with the change from baseline at each subsequent visit. If a result is below the limit of quantification, it will be set to half the value for analysis (e.g., “< 3” will be analyzed as 1.5). The International System of Units (SI) will be used for all summaries.

Abnormal chemistry, hematology, urinalysis, and urine microscopy results for each subject will be provided in listings that will include laboratory test name, result, normal range, and an explanation for clinically significant values.

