10.3 Vital Signs and Weight

Weight and vital signs (including systolic blood pressure, diastolic blood pressure, pulse rate, respiratory rate, and body temperature) will be summarized for each treatment group. Descriptive statistics of each parameter at baseline will be provided along with the change from parent-study baseline at each subsequent visit. A subject-level listing will also be provided.

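### No planned table gives the number of subjects with any clinically significant lab or vital-sign change, although that is a named safety endpoint

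*SAP*

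**What the plan says.** **Endpoint.** Protocol 3.2.1 names "Clinically significant changes from parent-study-baseline clinical laboratory measures and vital signs, as assessed by the Investigator, over the course of the study". SAP 3.2.3, item 2, repeats it with an end point at Visit 3E (Week 48). AEs and SAEs are a separate item in both lists.

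**Labs.** Under SAP 10.2, results from the central laboratory are "summarized into shift tables as normal, non-clinically significant abnormal, and clinically significant abnormal". The sentence covers all chemistry, hematology and urinalysis results. The unit of count then follows: "Shift tables will compare the number and percent of assessments from each visit to baseline values for each treatment group".

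**Vital signs.** SAP 10.3 plans this: "Descriptive statistics of each parameter at baseline will be provided along with the change from parent-study baseline at each subsequent visit". A subject-level listing is added. Clinical significance is not mentioned.

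**Unscheduled data.** SAP 7.1 sets a general rule: "Data collected from unscheduled visits will not be included in summary tables". The same sentence keeps these data in listings by subject, as appropriate. Neither SAP 10.2 nor SAP 10.3 makes an exception to the rule.

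**AE route.** Protocol 7.1.1 and 7.2.1 and SAP 7.4.2 require a clinically significant lab result or vital sign to be recorded as an AE. SAP 10.1 tabulates AEs by unique subject within periods bounded by the study injections.

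**The concern.** An endpoint defined over a period calls for a count of subjects affected at any time in that period. The planned tables give something else.

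- **Labs.** By-visit rows cannot be added up to subjects, because the tables do not show who is abnormal at more than one visit. A result obtained only at an unscheduled visit is in no row.
- **Vital signs.** The tables never use the investigator's judgement of significance, which is what the endpoint is about.

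Protocol 7.1.1 gives one reason why off-schedule data may exist: "The subject may be asked to return to the site for an unscheduled visit if an AE occurs between study visits", where the investigator thinks the event needs a visit for full evaluation. If labs are drawn then, they come from subjects who are having events, so they are among the more informative results.

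At stake is whether a reader of the study report can see, by arm, how many subjects had a significant lab or vital-sign change, without rebuilding the count from listings.

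**Working it through.** The documents give no rate, power or precision figure for this endpoint. The sample size of up to approximately 500 rests on practical considerations (SAP 5). There is therefore no planned figure to reproduce, and the check is a comparison of texts followed by a counting illustration.

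**Step 1: what each planned output provides.**

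| Output | Unit counted | Clinical significance shown | Unscheduled results | Any-time subject count for the endpoint |
|---|---|---|---|---|
| Lab shift tables (SAP 10.2) | Assessments per visit | Yes | Excluded by SAP 7.1 | No |
| Vital-sign summaries (SAP 10.3) | Values and changes per visit | No | Excluded by SAP 7.1 | No |
| Listings (SAP 7.1, 10.2, 10.3) | Individual results | Explanation given for labs | Included as appropriate | No |
| AE tables (SAP 10.1) | Unique subjects per AE, by period | Indirectly | Included, whatever the visit type | No, not grouped as labs or vital signs |

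**Step 2: the internal tension.** SAP 10.2 says all central-lab results go into the shift tables. SAP 7.1 keeps unscheduled results out of every summary table. Nothing says which sentence governs.

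**Step 3: off-schedule Termination Visit labs.** Labs are drawn at the Termination Visit (Protocol 7.3.3; SAP 7.4.3). SAP 7.1.3 attaches early-termination assessments to a visit only if they coincide with a scheduled one, and only for FAS analysis. Safety tables use the Safety Analysis Set (SAP 10). Final labs from a subject who leaves between visits have no stated place in a by-visit table.

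**Step 4: size, as an illustration for labs.**

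Inputs:
- Two scheduled draws in this study up to Visit 3E, at Visits 2E and 3E (SAP 7.4.3).
- *N* = 500, both arms together (SAP 5).
- Assumed: the proportion *p* with a clinically significant result is the same at both visits, and all subjects attend both. I use *p* = 2%.
- Assumed: a share *u* of affected subjects is seen only at unscheduled visits, from 0 to 30%.

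Formulas:
- One visit row shows *Np* = 500 × 0.02 = 10 subjects.
- Subjects ever affected range from *Np*/(1 − *u*), if the same subjects are abnormal at both visits, to 2*Np*/(1 − *u*), if none are.
- The share visible in one row therefore lies between (1 − *u*)/2 and (1 − *u*).

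| *u* | Subjects ever affected | Share shown by one visit row |
|---|---|---|
| 0 | 10 to 20 | 50-100% |
| 10% | 10/0.9 = 11.1 to 20/0.9 = 22.2 | 45-90% |
| 30% | 10/0.7 = 14.3 to 20/0.7 = 28.6 | 35-70% |

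Over the whole range, one row shows 35-100% of the subjects ever affected. Because *N* and *p* cancel, *p* = 1% or 5% gives the same shares.

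**The case against.** The strongest reply is that the AE tables already do the work. Every clinically significant lab result or vital sign is to be recorded as an AE, and AEs are counted by unique subject whatever the type of visit. The first AE period ends at the second injection in this study, which is close to the endpoint's limit at Visit 3E. Abnormal labs are also listed with an explanation of the significant ones, and vital signs are listed by subject.

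This defeats one tempting inference, that such findings go uncounted or disappear. They do not. It does not supply the endpoint, for three reasons. Protocol 7.1.1 prefers a diagnosis as the AE term, so a lab finding may sit under a disease. No AE table groups lab or vital-sign findings. And the SAP lists the two endpoints separately without saying that one is reported through the other.

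Three further limits stand:

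- A reader might infer that a large vital-sign change would be invisible because only averages are shown. SAP 7.1 includes the minimum and maximum, so a large change at a scheduled visit would normally appear there.
- A reader might infer that unscheduled visits routinely produce labs. Protocol 7.1.1 only says that a subject may be asked to return, and Protocol 7.2.1 lists scheduled collections alone.
- A reader might put the gap as lost power to show a difference between arms. SAP 10 plans no formal safety tests. Such a figure would also need assumed event rates, independence between visits and an assumed excess of unscheduled findings on LOR. If the same subjects are abnormal at both visits and nothing is found only off schedule, one row already holds everyone.

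**Conclusion.** The point holds as a reporting gap. A named safety endpoint has no table that gives the number of subjects affected, and SAP 7.1 and SAP 10.2 disagree on whether unscheduled central-lab results are summarised. Undercounting is a fair description of a lab visit row taken as the endpoint count, but not of the safety reporting as a whole.

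The 35-100% range depends on the assumed share seen only at unscheduled visits and on the overlap between visits, neither of which the documents give. It shows how far a visit row could fall short, not how far it will. Severity is minor: the endpoint is descriptive, and the underlying findings reach the AE tables and listings.

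**What to change.** **SAP 10.2.** Add a shift table, by arm, of each subject's worst post-baseline lab category (normal, abnormal but not clinically significant, clinically significant). Include unscheduled and off-schedule Termination Visit central-lab results. Present it for the period up to the Visit 3E injection and for the period after it. For placebo subjects who cross over, state the reference value for the second period; Protocol 10.4.2 uses Visit 3E.

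**SAP 7.1.** Exempt this table from the exclusion of unscheduled data, which also resolves the tension with SAP 10.2.

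**SAP 10.3.** Add the number and percent of subjects with any clinically significant vital-sign finding in each period. The documents describe no separate flag for this, so where none exists take it from the AE records.

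**Keep** the by-visit tables as planned.

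**Cost.** A few lines of SAP text and one or two extra tables from data already held. Worst-value tables will show slightly higher abnormality rates in both arms, which a footnote can explain.
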